Grade 4 Diarrhea or Colitis (Life threatening)	
 • Hospitalize and promptly start supportive treatment • Consider endoscopy and GI consult, as needed • Evaluate differential diagnosis and causality (as described above) • Prompt treatment with systemic steroids such as 1 to 2 mg/kg/day IV methylprednisolone or equivalent and/or empiric antibiotics 	Withhold study drug	
 • Continue close follow-up until resolution • Once resolved, start with reduced dose • If immune mediated, permanently discontinue study drug and promptly start steroid treatment with gradual steroid tapering • Monitor closely on restarting treatment of the diarrhea/colitis regardless of whether infectious or immune mediated; if at the reduced dose, the symptoms recur at Grade 3 or higher, then permanently discontinue the study drug

CMV = cytomegalovirus; COVID-19 = coronavirus 2019; CTCAE = Common Terminology Criteria for Adverse Events; GI = gastrointestinal; IV = intravenous; RT-PCR = real-time polymerase chain reaction.

Table 8 Dose Modification/Toxicity Management Recommendations for Hepatic Adverse Events

Adverse Reaction CTCAE v5.0 Grade/Severity	Recommended Management	Recommended Dosing Modification	Recommended Follow-up
Grade 1 or 2 AST/ALT elevation (≤5 times upper limit of the normal [ULN] or from baseline, if baseline is abnormal)	
 • Evaluate differential diagnosis and causality (including pre-existing liver disease and infectious etiology including possible COVID-19 infection [use RT-PCR for diagnosis]) • Close monitoring for worsening of any clinical signs/symptoms (eg, hyperbilirubinemia) • Close monitoring of transaminase and bilirubin levels until return to Grade 1 or < 3 times ULN • Manage with supportive care for symptom control • If the AST/ALT and bilirubin levels meet the definition of Hy's law, permanently discontinue the study drug 	Continue current dose	
 • Monitor as clinically indicated and initiate treatment as per standard of care.

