Grade 3 or 4 AST/ALT elevation (> 5 to 20 times ULN or from baseline, if baseline is abnormal)	
 • Evaluate differential diagnosis and causality (including pre-existing liver disease and infectious etiology) • Close monitoring for any clinical symptoms • Weekly monitoring of transaminase and bilirubin levels until return to Grade 1 or < 3 times ULN • Consider hepatic consult and treat accordingly per standard treatment guidelines • Permanently discontinue study drug if the patient meets the definition of Hy's law 
 ○ AST or ALT value > 3 × ULN and TBL > 2 × ULN ○ No other reason to explain combination of increased AST or ALT and TBL, ALP normal (ie, no initial findings of cholestasis) 	Withhold study drug	
 • If resolved to Grade 1 or baseline in less than 28 days, resume study drug at the same or a reduced dose at the discretion of the investigator • If not resolved to Grade 1 or baseline more than 28 days recommend restarting at a reduced dose • In case of Hy's Law or if suspicious of liver injury permanently discontinue study drug

ALP = alkaline phosphatase; ALT = alanine aminotransferase; AST = aspartate aminotransferase; COVID-19 = coronavirus 2019; CTCAE = Common Terminology Criteria for Adverse Events; RT-PCR = real-time polymerase chain reaction; TBL = total bilirubin level; ULN = upper limit of normal.

Table 9 Dose Modification/Toxicity Management Recommendations for Infection

Adverse Reaction CTCAE v5.0 Grade/Severity	Recommended Management	Recommended Dosing Modification	Recommended Follow-up
Grade 1 or 2 Infection	
 Evaluate differential diagnosis and causality (infection/immune-related/disease progression) with standard diagnostic tests (including but not limited to imaging, COVID-19 testing, chest X-ray, cultures, etc) Consider supportive care, including use of growth factors for patients with persistent or severe myelosuppression Once confirmed as infection, treat as per standard guidelines (including but not limited to antibiotics or antifungals) Consider infectious disease consult, as appropriate For patients with pulmonary or GI toxicities or myelosuppression, also refer to guidelines for management of those conditions 	Continue current dose	
 In case of persistent infection or worsening, manage as next higher grade

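### For AST/ALT above 5x ULN with bilirubin above 2x ULN, Table 8 and Appendix 13 disagree on resuming the drug and on how often to test, and Table 8 does not point to Appendix 13

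*Protocol*

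**What the plan says.** Section 5.4.3 refers sites to Appendix 15 for managing identified toxicities, hepatic toxicity included, and for the related dose changes. The hepatic table there is Table 8.

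The Grade 3 or 4 row of Table 8 covers AST/ALT above 5 times ULN. Its dosing instruction is to withhold. Its testing instruction is "Weekly monitoring of transaminase and bilirubin levels until return to Grade 1 or < 3 times ULN". It requires permanent discontinuation if Hy's law is met, and defines Hy's law in two parts: AST or ALT above 3 times ULN with total bilirubin above 2 times ULN, and "No other reason to explain combination of increased AST or ALT and TBL, ALP normal (ie, no initial findings of cholestasis". For other patients in the row it says "If resolved to Grade 1 or baseline in less than 28 days, resume study drug at the same or a reduced dose", at the investigator's discretion, and "If not resolved to Grade 1 or baseline more than 28 days recommend restarting at a reduced dose". The last line discontinues permanently in a Hy's law case "or if suspicious of liver injury permanently discontinue study drug".

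Appendix 13 deals with possible drug-induced liver injury. Its trigger is ALT or AST above 3 times ULN together with bilirubin above 2 times ULN, which it calls the biochemical criteria for Hy's Law. There is no condition on ALP or on other causes. On that trigger the drug is discontinued immediately, bilirubin, ALP, AST and ALT are measured two to three times a week, and other causes are then evaluated. One paragraph continues the frequent tests until values are back to baseline or normal. The long-term follow-up paragraph continues them until the ALT/AST abnormality is stable or has recovered, and then hands back to the protocol.

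Section 6.2.3 (events of special interest) cites Appendix 13. Table 8, the introduction to Appendix 15 and Section 5.4.3 do not.

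**The concern.** The two appendices use the same transaminase and bilirubin cut-offs but treat another explanation differently. In Table 8, a raised ALP or another cause takes the patient out of the Hy's law definition, and so out of mandatory permanent discontinuation. In Appendix 13, other causes are investigated after the drug has been stopped, and the stop does not depend on the answer.

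The patients for whom this matters are plausible here. Exclusion criterion 3 admits patients with known Gilbert's disease and bilirubin up to 3 times ULN and, in the expansion stage, patients with documented liver infiltration and AST/ALT up to 5 times ULN. In such patients another explanation may well be offered.

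Hepatotoxicity is an important identified risk in Section 2.3.2.1 and an event of special interest in Section 6.2.3. A site that follows the dose-modification route (Section 5.4.3, then Table 8) meets the less strict text and is not told that the stricter one exists. At stake are re-exposure to the drug after a combined transaminase and bilirubin rise, and less frequent testing while the values are abnormal.

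**Working it through.** No design figure is involved, so there is no plan figure to reproduce. The check sets the two texts side by side and applies them to one patient.

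| | Table 8, Grade 3 or 4 row | Appendix 13 |
|---|---|---|
| Laboratory trigger | AST/ALT >5x ULN for the row; >3x with bilirubin >2x ULN for the Hy's law part | ALT or AST >3x with bilirubin >2x ULN |
| Further condition for stopping | No other explanation and normal ALP, or suspected liver injury | None |
| Immediate dosing action | Withhold | Discontinue |
| Resumption | Same or reduced dose if resolved in under 28 days; reduced dose recommended if not | No rule stated |
| Tests named | Transaminases and bilirubin | ALT, AST, ALP and bilirubin |
| Frequency | Weekly | Two to three times a week |

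**Assumed patient.** Normal baseline values; ALT 6x, bilirubin 2.5x and ALP 1.5x ULN; investigator does not suspect liver injury.

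1. Row: 6 > 5, so the Grade 3 or 4 row applies.
2. Laboratory pair: 6 > 3 and 2.5 > 2, so the shared cut-offs are met in both texts.
3. Table 8, second part: ALP 1.5x > 1x ULN is not normal, so Table 8's Hy's law definition is not met. The drug is withheld and may be resumed.
4. Appendix 13: step 2 is enough. The drug is discontinued immediately, whatever the ALP.
5. Testing: weekly is one test per 7 days. Two to three per week gives intervals of 7/2 = 3.5 days down to 7/3 = 2.3 days.

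**Same patient, but normal ALP and no other cause.** Table 8's definition is now met, so both texts stop the drug. Table 8 still lists weekly tests against two to three times weekly. The testing difference therefore does not depend on ALP or cause; the resumption difference does.

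**Limit from Section 5.4.2.** After the DLT window in Stage 1, and in Stage 2, an interruption for toxicity of more than 14 consecutive days leads to discontinuation unless investigator and sponsor agree otherwise. Under Table 8, resumption within 14 days is therefore open; resumption between day 15 and day 28, and the restart after 28 days, need that agreement.

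**The case against.** The strongest reply is that the texts serve different purposes and can both be followed. Table 8 is graded on AST/ALT, and Appendix 15 calls itself general guidance to be supplemented by protocol-specific instructions. Appendix 13 is the specific procedure for possible liver injury, and Section 6.2.3 sends readers there by name. Section 6.4.5 describes Hy's Law as excluding cholestasis and other causes of raised bilirubin, so Table 8's second condition agrees with the protocol body, while Appendix 13 deliberately acts earlier. A patient with these values must also be reported as an event of special interest, so an investigator may well suspect liver injury and discontinue under Table 8's own last line. Testing two to three times a week also satisfies a weekly requirement.

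Much of this stands. A careful site can follow the stricter rule, and the assumed patient is treated differently only because liver injury is taken as not suspected. But suspicion is a judgement, whereas Appendix 13 acts on laboratory values. Section 6.4.5 governs reporting, not dosing or test frequency. No text says which appendix prevails.

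A reader might go further and infer that Appendix 13 forbids rechallenge. It does not say so: it discontinues immediately, without the word permanently that Appendix 15 uses when it bars re-dosing, and it ends by returning to the protocol. Its position on resumption is silence, not prohibition.

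**Conclusion.** The inconsistency is real and minor. For AST/ALT above 5x with bilirubin above 2x ULN, Table 8 tests less often than Appendix 13. When ALP is raised or another cause exists, and liver injury is not suspected, it also allows resumption of a drug that Appendix 13 has discontinued. Dosing stops at once under both. Section 4.5 puts about 3 patients on treatment at Amendment 5, enrollment is closed, and no endpoint or planned analysis changes. The conclusion rests on reading the rows as printed; the patient values are assumptions.

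Three stronger readings are not supported:

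- A reader might infer that a Grade 2 patient (say ALT 4x, bilirubin 2.5x, ALP 1.5x ULN) continues dosing under Table 8. The Grade 1 or 2 row says "If the AST/ALT and bilirubin levels meet the definition of" Hy's law and names those levels only, with no ALP or other-cause condition. Its natural reading agrees with Appendix 13 on stopping the drug. It gives no test frequency ("Close monitoring of transaminase and bilirubin levels until return to Grade 1 or < 3 times ULN"), so a pointer would still help.
- A reader might infer that Table 8's testing end-point is sometimes earlier and sometimes later than Appendix 13's. That appears only by switching between Appendix 13's two end-points. With normal baselines, ALT stable at 4x ULN satisfies the stable-or-recovered wording but not the baseline-or-normal wording. What remains is that Appendix 13 has two end-points.
- A reader might infer from "Grade 3 or 4 AST/ALT elevation (> 5 to 20 times ULN or from baseline, if baseline is abnormal" that values above 20x ULN are left without instruction. The row label covers Grade 4, and Section 2.3.2.1 withholds for any hepatic event of Grade 3 or higher.

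**What to change.** In the Grade 3 or 4 row of Table 8:

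- For ALT or AST >3x ULN with bilirubin >2x ULN, replace the weekly-testing and dosing instructions with: discontinue immediately and follow Appendix 13, with tests two to three times a week.
- Limit the resume and restart lines to patients who do not meet these values. Without this, the contradiction would sit inside a single row.
- Keep the no-other-reason and normal-ALP condition only as the criterion for permanent discontinuation once the work-up is complete, and add one sentence saying whether dosing may resume if another cause is confirmed.

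In the Grade 1 or 2 row, add a reference to Appendix 13. In Appendix 13, choose one end-point for the frequent tests: either baseline or normal, or stable or recovered.

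The cost is a few sentences in two appendices. No new procedure is needed, because Appendix 13 already requires the tests.

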APPENDIX 18 AMENDMENT HISTORY

Amendment 4 (12 December 2022)

Section Number	Summary of Change	Rationale for Change
Cover Page, Sponsor’s Approval, Document History, Header, and Footer	Administrative updates made to reflect Amendment 4	The administrative updates were made to reflect Amendment 4.
Section 2.1 – Current Therapies and Unmet Medical Need	Additional text added to review the use of BCL-2 inhibitor therapy in CLL and definition of double refractory CLL	This information clarifies the current treatment landscape in CLL and provides background for requirement for prior BCL-2 inhibitor therapy in selected patients in the post-BTK CLL cohort.
Section 2.2.3 – Nonclinical Toxicology	Additional text added to update results of in vitro phototoxicity studies	Based on updated data
Synopsis, Section 4.5 – Dose Expansion Stage (Stage 2)	
Language was added to indicate that as of 30 November 2022, patients will no longer be permitted to consent to enroll in selected lymphoma dose expansion cohorts (mantle cell lymphoma [MCL], follicular lymphoma [FL], marginal zone lymphoma [MZL], Waldenström’s macroglobulinemia/lymphoplasmacytic lymphoma [WM/LPL], peripheral T-cell lymphoma [PTCL], and cutaneous B-cell lymphoma [CBCL]. Currently enrolled patients deriving clinical benefit from treatment may continue to participate in the study.
 
The dose expansion cohort for chronic lymphocytic leukemia (CLL) post-Bruton tyrosine kinase (BTK) exposure is also modified to require approximately 10 out of 20 patients to have received prior Bcell lymphoma-2 (BCL-2) inhibitor therapy in addition to the BTK therapy.
	
This new language confirms that consenting to the study, for selected cohorts was halted on 30 November 2022. This language also confirms this change is not based on any patient safety or efficacy concerns, and to ensure patients deriving clinical benefit from study treatment may continue treatment.
 
Based on emerging unmet need in the clinic for the management of patients who have failed both BTK and BCL-2 targeted therapies, so called “double refractory” patients

Synopsis, Section 4.7.2 – Rationale for Selection of Patient Population, Section 5.1.1 – Inclusion Criteria	Language regarding closing enrollment to all non-Hodgkin’s lymphoma (NHL) expansion cohorts added.	This language was added to reflect changes in patient enrollment upon implementation of this protocol amendment.
Synopsis, Section 4.8.3 – Pharmacokinetic Outcome Measures	Removed bullet “The Accumulation Index based on area under the concentration time curve (AUC)”	Clarification
Section 5.4.3 – Recommendations for Management of Toxicity Including Dose Modification	Removed phototoxicity management/sunlight precautions	Results of the in vitro phototoxicity studies with HMPL-523 CCI [REDACTED] CCI [REDACTED] showed no phototoxic potential, indicating

Section Number	Summary of Change	Rationale for Change
		that the previously necessary precautions in this clinical study can be lifted.
Synopsis, Section 7.1 – Determination of Sample Size, Section 7.1.2 – Stage 2: Dose Expansion	Language was added to confirm the total expected enrollment is approximately 90 patients and approximately 70 patients are expected to enroll in the Dose Expansion Stage (stage 2). Language associated with the change in expected enrollment was removed or updated for clarity.	The new language confirms the expected enrollment upon completion of enrollment upon implementation of this protocol amendment.
Section 7.2 – Analysis Population	Text added defining DLT evaluation	Based on updated data
Synopsis, Section 7.3 – Analysis Planned, Section 7.3.1 – Demographic and Baseline Characteristics, Section 7.3.2 – Disposition of Patients Enrolled in the Study, Section 7.3.3 – Safety Analysis, Section 7.3.3.2 – Adverse Events, Section 7.3.3.3 – Clinical Laboratory Test Values, Section 7.3.3.4 – Vital Signs, Section 7.3.3.5 – 12-Lead ECGs, Section 7.3.5 – Efficacy Analysis	Any language, headings, tables, and analyses related to assessments, objectives, and endpoints that fall outside of the scope of the necessary assessments for the Safety Review Committee to monitor the benefit/risk profile of patients remaining on trial were updated or removed.	This language was updated or removed to clarify what assessments, objectives, and endpoints are still relevant upon implementation of this protocol amendment.

Amendment 3 (23 July 2022)

Section Number	Summary of Change	Rationale for Change
Section 2.1 – Current Therapies and Unmet Medical Need Section 2.2.2 - Nonclinical Pharmacokinetics Section 2.2.3 - Nonclinical Toxicology Section 2.2.4 – Clinical Experience Section 2.3.2.1 – Risk Assessment	Updated based on Investigator’s Brochure (IB) v9.	To provide updated information.
Section 4.5 Dose Expansion Stage (Stage 2)	Overall expansion stage enrollment increased from 110 to 125. Increased number of patients in Hodgkin’s lymphoma (HL) cohort of expansion stage from 10 to 25.	To increase the sample size of the HL dose expansion cohort to further evaluate the efficacy and safety of HMPL-523 in these patients.
Section 4.7.1 - Rationale for the Starting Dose and the Dose Schedule	Updated status of studies as of 10 May 2022.	To provide updated information.
Section 5.1.1 – Inclusion Criteria #4	Added number of subjects for HL cohort.	To increase the sample size of the HL dose expansion cohort to further

Section Number	Summary of Change	Rationale for Change
		evaluate the efficacy and safety of HMPL-523 in these patients.
Section 5.1.2 – Exclusion Criteria #2	Note has been updated to clarify patients with low complete blood cell count can be enrolled if they have splenic involvement or bone marrow infiltration.	To allow splenic involvement or bone marrow infiltration as condition with sponsor approval to make exception for lower blood counts.
Section 5.1.2 – Exclusion Criteria #14 Appendix 1 – Schedule of Activities Appendix 13 Clinical Evaluation of Possible Drug-Induced Liver Injury	Added cytomegalovirus (CMV) test at screening.	To provide clarification that CMV viral antibody test should be performed at screening to ensure CMV DNA testing is negative to enroll patients.
Section 5.1.2 – Exclusion Criteria #18 Section 5.5.2 – Prohibited Therapy and Food Appendix 16 - Prohibited Concomitant Medications that Have a Known Risk of QT prolongation and/or Torsades de Pointes (TdP)	Reference to http://www.crediblemeds.org removed and appendix has been added.	For clarification on prohibited concomitant medications that have a known risk of QT prolongation and/or TdP.
Section 5.4.3 and Appendix 15 Recommendations for Management of Toxicity Including Dose Modification	Added new section and appendix on recommendations for management of toxicity including dose modification.	To provide guidelines for management of toxicities including dose modifications.
Section 5.5.2 – Prohibited Therapy and Food	Updated the section.	To provide updated information based on findings and interpretation of in vitro drug-drug interaction studies.
Section 5.6.9 – Laboratory Assessments	Added CMV testing at screening. Removed reticulocyte count and bands as part of differential white blood cells count.	For clarification. Reticulocyte count and bands are not part of routine complete blood count at many sites.
Section 5.6.10 – Electrocardiogram Appendix 1 – Schedule of Activities	Electrocardiogram to be performed at screening and at Cycle 1, Day 1.	For clarification.
Section 5.7.3 – Study Treatment Discontinuation	Added cross reference to Section 5.5.2	For clarification.
Section 5.9.3 – Analytical Procedures	Updated the method for determination of chemokines.	For clarification.
Section 6.2.3 – Protocol-Defined Events of Special Interest Expedited Adverse Events	Added adverse events of special interest.	For clarification.
Section 7.1 – Determination of Sample Size Section 7.1.2 Stage 2: Dose Expansion	Planned enrollment for this study was updated from approximately 116 to 140 patients to approximately 131 to 155 patients.	To increase the sample size of the HL dose expansion cohort to further evaluate the efficacy and safety of HMPL-523 in these patients.

Section Number	Summary of Change	Rationale for Change
	Increased number of patients in HL cohort as noted above for Section 4.5. Sample size increased from 110 to 125 patients. Probability of observing at least 1 adverse event in expansion stage patients was updated.	
Section 7.2 – Analysis Population	Definition of response evaluable set (RES) updated.	For clarification.
Appendix 7 – Lists of Prohibited Drugs and Those That Should Be Used with Caution	Renamed/revised appendix and added P-gp, BCRP, and MATE1/2-K sensitive substrates and substrates with narrow therapeutic range.	To avoid confusion and protocol deviations for prohibited concomitant medications and to specify that the substrates with narrow therapeutic range are prohibited.
Throughout the protocol	Administrative changes made throughout the protocol.	To update company name, address, company logo, and amendment version.
Throughout the protocol	Minor grammatical, formatting, and revisions were made throughout the protocol.	For better presentation.

Amendment 2 (07 August 2021)

Section Number	Summary of Change	Rationale for Change
Section 4.5 - Dose Expansion Stage (Stage 2)	Overall expansion stage enrollment increased from 70 to 110. Addition of new cohorts: CLL/SLL post-BTK exposure (n = 20) and HL (n = 10). Increased number of patients in FL cohort of expansion stage from 10 to 20. Add identified RP2D (700 mg once daily).	To add a dose expansion cohort and increase the sample size of an existing dose expansion cohort to further evaluate the efficacy and safety of HMPL-523 based on proof of activity from a Phase I study in China evaluating HMPL-523 in lymphoma patients. For information.
Section 4.4.5 - Definition of Recommended Phase II Dose	Added identified RP2D (700 mg once daily).	For information.

Section Number	Summary of Change	Rationale for Change
Section 7.1 - Determination of Sample Size Section 7.1.2 - Stage 2: Dose Expansion	
Addition of new CLL/SLL post-BTK exposure and HL cohorts and increased number of patients in FL cohort as noted above for Section 4.5.
 
Provided updated probability of observing a given adverse event based on increase in number of patients in expansion phase.
 
Sample size (planned enrollment) corrected to 116-140 patients.
	
To add a dose expansion cohort and increase the sample size of an existing dose expansion cohort to further evaluate the efficacy and safety of HMPL-523 based on proof of activity from a Phase I study in China evaluating HMPL-523 in lymphoma patients.
 
To be consistent with 6-30 patients from dose escalation stage + 110 patients from dose expansion.

Section 2.2.4 - Clinical Experience Section 4.7.1 - Rationale for the Starting Dose and the Dose Schedule	Removed location “Australia” for 2015-523-00CH1, which was conducted in China.	For correction.
Section 2.2.4.5 - Study 2018-523-00US1 Phase I Study in Patients with Relapsed/Refractory Lymphoma	Subsection added to describe the rationale for adding the chronic lymphocytic leukemia/small lymphocytic lymphoma (CLL/SLL) post-Bruton’s tyrosine kinase (BTK) exposure and Hodgkin lymphoma (HL) cohorts and increasing number of patients in follicular lymphoma (FL) cohort.	To provide rationale for additional expansion phase cohorts and to have a larger cohort to further evaluate the efficacy of HMPL-523 in FL.
Section 2.1 - Current Therapies and Unmet Medical Need	Added background regarding spleen tyrosine kinase expression in HL patients.	To provide rationale for addition of HL cohort.
Section 4.5.1 - Exploratory Analysis	Section deleted and content moved to Section 5.9.	To present sub-section in Section 5.9 for a better flow as the exploratory biomarker analysis applies to the entire study and not just the dose expansion stage.
Section 5.4.2 - After Dose-Limiting Toxicity Assessment Window in Stage 1 or in Stage 2	
Specified 600 mg and 400 mg dose as the first and second lower dose in case of toxicity.
 
Added statement to consult with Sponsor if treatment hold longer than 2 weeks is required for resolution of toxicity.
 
Add requirement for additional PK sampling if dose is reduced for toxicity in Stage 2.
	
For clarification.
 
To allow longer window for toxicity resolution.
 
To evaluate relationship of PK data to observed toxicity.

Section 5.6.9 - Laboratory Assessments	Removed description of pharmacokinetic (PK) and pharmacodynamic assessments.	To minimize redundancy as these assessments are addressed separately under Section 5.9.

Section Number	Summary of Change	Rationale for Change
Section 5.9 - Pharmacokinetic and Pharmacodynamic Assessments	
Revised/reorganized section. Previously Section 5.9 title was “Assay Methods.”
 
Included and updated text regarding exploratory analyses that was previously in Section 4.5.1.
 
Reference to central laboratory removed.
 
Method for analysis of plasma samples (Liquid Chromatography-Tandem Mass Spectrometry) identified.
	To streamline and update the content.
Section 5.9.1 - Collection Schedule	
Included collection of additional PK and pharmacodynamic samples for steady state reached with new dose after treatment hold for toxicity.
 
Specified purpose for blood samples that remain after PK analysis.
 
Include statement that tumor biopsy (archival or fresh biopsy) will be collected at screening for patients in dose expansion cohorts.
 
Specified purpose for tumor samples that remain after predefined analysis.
	
To evaluate relationship of PK data to observed toxicity.
 
For clarification.
 
To allow evaluation of candidate biomarkers.
 
For clarification.

Section 5.1.1 - Inclusion Criteria # 7	Added requirement for availability of tumor sample (archival or fresh biopsy) for patients in dose expansion cohorts.	To allow evaluation of candidate biomarkers.
Section 4.7.1 - Rationale for the Starting Dose and the Dose Schedule	
Updated study status of clinical trials discussed.
 
Updated Table 2 data.
	
To provide updated study status.
 
To provide corrected data.

Section 4.7.2 - Rationale for Selection of Patient Population	
Listed patients with CLL post-BTK exposure and HL with the rest of the cohorts.
 
Replaced term “NHL” with “lymphoma.”
	
To include new cohorts.
 
To use more general term, since HL cohort has been added.

Section 5.3.5 - Post-Trial Access to HMPL-523	Replaced term “NHL” with “lymphoma.”	To use more general term, since HL cohort has been added.

Section Number	Summary of Change	Rationale for Change
Section 4.8.3 - Pharmacokinetic Outcome Measures	Removed following PK parameters: 
 • Terminal half-life • Apparent volume of distribution based on the terminal phase • Mean residence time • Mean plasma concentration 	To update list of PK parameters.
Section 7.3.4 - Pharmacokinetic Analysis	Listed PK parameters updated as for Section 4.8.3. Added statement that statistical or PK analysis plan will source for details of PK analysis. Specified that HMPL-523 CCI concentrations will be plotted by dose level.	To update list of PK parameters and related endpoints. For clarification. For clarification.
Section 5.1.1 - Inclusion Criteria #4	Addition of CLL/SLL post-BTK exposure and HL cohorts.	To further evaluate the efficacy and safety of HMPL-523.
Section 5.1.1 - Inclusion Criteria #6	Clarified the definition of measurable disease to align with Lugano criteria: nodal disease > 1.5 cm, non-nodal disease > 1 cm. Added HL to disease subtypes listed in text describing measurable disease definition.	For consistency with Lugano criteria as the measurable disease was defined as > 1.5 cm. To include HL, as an HL cohort has been added to study.
Section 5.1.1 - Inclusion Criteria #10	For contraception, specified that male patients must use condom. Clarified measures to be used are highly effective measures as defined by Clinical Trials Facilitation Group, provided additional information regarding route of administration and types of contraceptive methods. Updated duration of contraceptive use from 100 days to 30 days (based on updated investigator's brochure [IB]).	To align with updated recommendation in IB and to match other protocols.
Section 5.6.9 - Laboratory Assessments Appendix 1 - Schedule of Activities, footnote 16	Clarified definition of postmenopausal female.	
Section 5.1.2 - Exclusion Criteria #15	Listed urine test under pregnancy test.	For clarification.

Section Number	Summary of Change	Rationale for Change
Section 2.2.1 - Nonclinical Pharmacology Section 2.2.2 - Nonclinical Pharmacokinetics Section 2.2.3 - Nonclinical Toxicology	Updated based on IB v8.	To provide updated information.
Section 2.2.4 - Clinical Experience	Updated based on IB v8.	To provide updated information.
Section 2.3 - Study Rationale and Benefit-Risk Assessment	Added subheadings within section. Added important identified risks provided in IB v8. Added reference to Section 2.2.4.	To provide updated information.
Section 5.7.1 - Study Completion/Early Termination Visit	Replaced “TEAE” with “AE”. Added “Extended Monitoring” to “Follow-up” subheading.	For correction. For clarification.
Appendix 14 Coronavirus Disease 2019 (COVID-19) Risk Assessment and Vaccine Guidance (New Appendix)	Added appendix providing COVID-19 risk assessment and vaccine guidance.	For guidance on COVID-19 risk assessment and vaccination.
Section 5.1.2 - Exclusion Criteria #12	Added reference to COVID appendix.	
Section 5.5.2 - Prohibited Therapy and Food	Added restrictions and instructions on the use of acid-reducing agents. Added exception to grapefruit restriction based on Appendix 7.	To avoid co-administration of acid-reducing agents that may have a negative impact on the absorption of and decrease the bioavailability of HMPL-523 as the solubility of HMPL-523 is pH dependent. For clarification.
Section 5.6.2 - Informed Consent Forms and Screening Log Section 8.3 - Patient Information and Consent Section 8.4 - Data Privacy and Confidentiality	Included detailed information regarding data protection.	To comply with data privacy regulations/guidance.

Section Number	Summary of Change	Rationale for Change
Appendix 1 Schedule of Activities	
Added row for screening tumor biopsy for patients in dose expansion cohorts.
 
Added “pharmacodynamics” plasma sampling with PK plasma sampling under procedures.
 
Footnote 22 revised: “All” rather than “some” expansion patients will provide samples for PD analysis; text regarding basis for defining scope of PD assessment and determination of PD sampling time points is deleted.
 
Replaced “Cycle 1 Day 1” with “screening” for Footnote 6.
	
For analysis of candidate biomarkers.
 
For clarification.

Appendix 2 PK Sampling Time Points (Once Daily) (Dose Escalation Stage) ^d	
Removed column for “Sample Volume.”
 
Added footnote “d” specifying that the remaining blood samples may be used exclusively for exploratory biomarker purposes.
	
To avoid duplication and discrepancy as the sample volume can be found in the PK laboratory manual.
 
For clarification.

Section Number	Summary of Change	Rationale for Change
Appendix 3 PK and Pharmacodynamics Sampling Time Points (Dose Expansion Stage) ^e	
Removed column for “Sample Volume.”
 
Added 2 new columns for additional trough PK and pharmacodynamics samples to be collected in the dose expansion phase.
 
Added additional PK and pharmacodynamic sampling visit day and timepoints after dose reduction due to toxicity.
 
Added footnotes “d” and “f” specifying recording of actual date and time of the PK samples in the electronic case report form, study drug intake at the investigative site under the supervision of the investigator or designee on PK sampling day.
 
Added footnote “e” to specify use of blood samples remaining after PK analysis for exploratory biomarker purposes.
 
Added footnote “g” for Cycle 1 Day 28 for PK sample rescheduling in case they are not collected as scheduled.
	
To avoid duplication and discrepancy as the sample volume can be found in the PK laboratory manual.
 
For analysis of long-term PK and pharmacodynamics results in patients receiving HMPL-523.
 
To evaluate relationship of PK data to observed toxicity.
 
For clarification.

Section 6.7 - Post-Study Adverse Events	Revised term “congenital anomaly” to “congenital anomaly/birth defect.”	For consistency with usage in other parts of protocol.
Section 6.4.10 - Pregnancy	Specified the last dose of the study drug as male patient’s last dose of the study drug.	For clarification.
Section 7.3.6 - Biomarker Analysis	Replaced the information for biomarker analysis plan document with a high-level summary of the analysis to be performed.	For correction as the biomarker analysis plan document is not available.
Appendix 15 - Amendment History (New Appendix)	Added summary of Amendment 1 changes to Amendment History.	For consistency with sponsor’s process and template.

Amendment 1 (09 April 2020)

Description and Rationale for Change	Sections
Updated the clinical cutoff date and inclusion of completed studies.	Section 2.2.4 Clinical Experience

Description and Rationale for Change	Sections
Ongoing studies have been updated to represent the appropriate countries.	
New section has been added for a Phase I open-label study to evaluate the safety, tolerability, pharmacokinetics, and preliminary efficacy of HMPL-523 in patients with relapsed or refractory lymphoma.	Section 2.2.4.5 Study 2018-523-00US1 Phase I Study in Patients with Relapsed/Refractory Lymphoma
Updated to reflect the deletion of the 1000 mg dose and keeping the 600 mg dose.	Section 2.3 Study Rationale
Added an exploratory objective to explore biomarkers	Section 3.3 Exploratory Objectives
Added ongoing study information and updated safety data from completed dose escalation studies.	Section 4.7.1 Rationale for the Starting Dose and the Dose Schedule
Added peripheral T-cell lymphoma (PTCL) and cutaneous B-cell lymphoma (CBCL) to types of lymphoma patients that will be enrolled	Section 4.7.2 Rationale for Selection of Patient Population Section 5.1.1 Inclusion Criteria
Route of administration has been added to specify: Orally, with water, after meal Removed pharmacokinetic data from dose escalation decision Removed potential for BID dosing	Section 4.2 Dose Escalation Stage (Stage 1) Table 1 Proposed Dose Escalation Scheme
New section has been added to specify eligibility criteria for patient intradose-escalation	Section 4.3 Inpatient Dose Escalation (new section)
Clarified definition of febrile neutropenia per CTCAE v5.0 and added criteria for Hy's Law	Section 4.4 Definition of a Dose Limiting Toxicity
Further clarified definition of DLT evaluable patients	Section 4.4.1 Dose Limiting Toxicity Assessment Window
Two additional cohorts have been added (PTCL and CBCL) with 10 patients planned for each of these cohorts. Revised the total number of patients from approximately 50 to approximately 70 patients with relapsed or refractory lymphomas	Section 4.5 Dose Expansion Stage (Stage 2) Section 5.1.1 Inclusion Criteria
Updated clinical trial information	Section 4.7.1 Rationale for the Starting Dose and the Dose Schedule
Added and clarified definitions of best overall response (BOR), time to response (TTR), and progression free survival (PFS).	Section 4.8.4 Efficacy Outcome Measures Section 7.3.5 Efficacy Analysis

Description and Rationale for Change	Sections

The inclusion criteria have been expanded to include the 2 additional cohorts: PTCL and CBCL.
 
Clarified the definition of relapsed and refractory lymphoma patients as:
 
 e. Refractory to any prior regimen, defined as no response (complete response [CR] or partial response [PR]) to previous therapies, or progression within 6 months of completion of the last dose of prior therapy. f. Those who can no longer tolerate/withstand cytotoxic chemotherapy and or available standard of treatment/care. Where safety profile and risks of toxicity of other treatment options far outweigh any possible clinical benefit g. Those with no curative standard of treatment or where available treatments are not reasonable or do not make sense. In particular, and in the opinion of the attending principal investigator, those who will benefit from this class of compound 
Contraceptive methods were clearly defined, and language has been added to describe highly effective measures.
 
Moved exclusion regarding prior SYK inhibitors to the inclusion criteria section for clarification of language
	
Section 5.1.1 Inclusion Criteria

